5.6.1.1 Supportive Care Guidelines for Immune-related Adverse Events (irAEs)

Events of clinical interest of a potential immunologic etiology (irECIs) may be defined as an adverse event of unknown etiology, associated with drug exposure and is consistent with an immune phenomenon. irAEs may be predicted based on the nature of the pembrolizumab compound, its mechanism of action, and reported experience with immunotherapies that have a similar mechanism of action. Special attention should be paid to AEs that may be suggestive of potential irAEs. An irAE can occur shortly after the first dose or several months after the last dose of treatment.

If an irAE is suspected, efforts should be made to rule out neoplastic, infectious, metabolic, toxin or other etiologic causes prior to labeling an adverse event as an irAE. Information on how to

identify and evaluate irAEs has been developed and is included in the Event of Clinical Interest and Immune-Related Adverse Event Guidance Document. See Section 12.6. Subjects who develop a Grade 2 or higher irAE should be discussed immediately with the Sponsor.

Recommendations to managing irAEs not detailed elsewhere in the protocol are detailed in Table 5.

Table 5 General Approach to Handling irAEs

irAE	Withhold/Discontinue Pembrolizumab?	Supportive Care
Grade 1	No action	Provide symptomatic treatment
Grade 2	May withhold pembrolizumab	Consider systemic corticosteroids in addition to appropriate symptomatic treatment
Grade 3 and Grade 4	Withhold pembrolizumab Discontinue if unable to reduce corticosteroid dose to < 10 mg per day prednisone equivalent within 12 weeks of toxicity	Systemic corticosteroids are indicated in addition to appropriate symptomatic treatment. May utilize 1 to 2 mg/kg prednisone or equivalent per day. Steroid taper should be considered once symptoms improve to Grade 1 or less and tapered over at least 4 weeks.

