5.8 Subject Withdrawal/Discontinuation Criteria

Subjects may withdraw consent at any time for any reason or be dropped from the trial at the discretion of the investigator should any untoward effect occur. In addition, a subject may be withdrawn by the investigator or the Sponsor if enrollment into the trial is inappropriate, the trial plan is violated, or for administrative and/or other safety reasons. Specific details regarding discontinuation or withdrawal are provided in Section 7.1.4 – Other Procedures. A subject must be discontinued from the trial for any of the following reasons:

- The subject or legal representative (such as a parent or legal guardian) withdraws consent.
- Confirmed radiographic disease progression after 12 weeks of treatment (see Table 7)

Note: A subject may be granted an exception to continue on treatment with confirmed radiographic progression if clinically stable or clinically improved, but [name] must be contacted first. If the subject has continued radiographic progression after the next set of 4 treatments OR clinical deterioration (such as increased pain) during the treatment, he must be removed from the study.

- Unacceptable adverse experiences as described in Section 5.2.1.2
- Intercurrent illness that prevents further administration of treatment
- Investigator's decision to withdraw the subject
- Noncompliance with trial treatment or procedure requirements
- The subject is lost to follow-up
- Administrative reasons

The End of Treatment and Follow-up visit procedures are listed in Section 6 (Protocol Flow Chart) and Section 7.1.5 (Visit Requirements). After the end of treatment, each subject will be followed for 30 days for adverse event monitoring (serious adverse events will be collected for 90 days after the end of treatment as described in Section 7.2.3.1). Subjects who discontinue for reasons other than progressive disease will have post-treatment follow-up for disease status until disease progression, initiating a non-study cancer treatment, withdrawing consent or becoming lost to

follow-up. After documented disease progression each subject will be followed by telephone for overall survival until death, withdrawal of consent, or the end of the study, whichever occurs first.

Patients will not be taken off study for PSA progression alone.

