7.1.5.3 Post-Treatment Visits

7.1.5.3.1 Safety Follow-Up Visit

The mandatory Safety Follow-Up Visit should be conducted approximately 30 days after the end of treatment visitor before the initiation of a new anti-cancer treatment, whichever comes first. All AEs that occur prior to the Safety Follow-Up Visit should be recorded. Subjects with an AE of Grade > 1 will be followed until the resolution of the AE to Grade 0-1 or until the beginning of a new anti-neoplastic therapy, whichever occurs first. SAEs that occur within 90 days of the end of treatment or before initiation of a new anti-cancer treatment should also be followed and recorded.

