All adverse events will be recorded from the time the consent form is signed through 30 days following cessation of treatment and at each examination on the Adverse Event case report forms/worksheets. The reporting timeframe for adverse events meeting any serious criteria is described in section 7.2.3.1.

Adverse events will not be collected for subjects during the pre-screening period (for determination of archival tissue status) as long as that subject has not undergone any protocol-specified procedure or intervention. If the subject requires a blood draw, fresh tumor biopsy etc., the subject is first required to provide consent to the main study and AEs will be captured according to guidelines for standard AE reporting.

7.2.1 Definition of an Overdose for This Protocol and Reporting of Overdose to the Sponsor and to Merck

For purposes of this trial, an overdose will be defined as any dose exceeding the prescribed dose for pembrolizumab by 20% over the prescribed dose. No specific information is available on the treatment of overdose of pembrolizumab. In the event of overdose, pembrolizumab should be discontinued and the subject should be observed closely for signs of toxicity. Appropriate supportive treatment should be provided if clinically indicated.

If an adverse event(s) is associated with (“results from”) the overdose of a Merck product, the adverse event(s) is reported as a serious adverse event, even if no other seriousness criteria are met.

If a dose of Merck’s product meeting the protocol definition of overdose is taken without any associated clinical symptoms or abnormal laboratory results, the overdose is reported as a non-serious Event of Clinical Interest (ECI), using the terminology “accidental or intentional overdose without adverse effect.”

All reports of overdose with and without an adverse event must be reported within 24 hours to the Sponsor and within 2 working days hours to Merck Global Safety. (Attn: Worldwide Product Safety; [contact])

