7.2.3 Immediate Reporting of Adverse Events to the Sponsor and to Merck

7.2.3.1 Serious Adverse Events

A serious adverse event is any adverse event occurring at any dose or during any use of Merck's product that:

- Results in death;
- Is life threatening;
- Results in persistent or significant disability/incapacity;
- Results in or prolongs an existing inpatient hospitalization;
- Is a congenital anomaly/birth defect;
- Is a new cancer (that is not a condition of the study);
- Is associated with an overdose;
- Is any other important medical event

Refer to Table 9 for additional details regarding each of the above criteria.

Progression of the cancer under study is not considered an adverse event unless it results in hospitalization or death.

Any serious adverse event, or follow up to a serious adverse event, including death due to any cause other than progression of the cancer under study that occurs to any subject from the time the consent is signed through 90 days following cessation of treatment, or the initiation of new anti-cancer therapy, whichever is earlier, whether or not related to Merck product, must be reported within 24 hours to the Sponsor and within 2 working days to Merck Global Safety. The clock begins at the time the study team learns of the event.

Non-serious Events of Clinical Interest will be forwarded to the Sponsor (OHSU) and to Merck Global Safety and will be handled in the same manner as SAEs.

Additionally, any serious adverse event, considered by an investigator who is a qualified physician to be related to Merck product that is brought to the attention of the investigator at any time outside of the time period specified in the previous paragraph also must be reported immediately to the Sponsor and to Merck.

SAE reports and any other relevant safety information are to be forwarded to the Merck Global Safety [contact]

A copy of all 15 Day Reports and Annual Progress Reports is submitted as required by FDA, European Union (EU), Pharmaceutical and Medical Devices agency (PMDA) or other local regulators. Investigators will cross reference this submission according to local regulations to the Merck Investigational Compound Number (IND, CSA, etc.) at the time of submission. Additionally investigators will submit a copy of these reports to Merck & Co., Inc. (Attn: Worldwide Product Safety; [contact]) at the time of submission to FDA.

All subjects with serious adverse events must be followed up for outcome.

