7.2.3.2 Events of Clinical Interest

Selected non-serious and serious adverse events are also known as Events of Clinical Interest (ECI) and must be recorded as such on the Adverse Event case report forms/worksheets and reported within 24 hours to the Sponsor and within 2 working days to Merck Global Safety. (Attn: Worldwide Product Safety; [contact])

Events of clinical interest for this trial include:

1. an overdose of Merck product, as defined in Section 7.2.1 - Definition of an Overdose for This Protocol and Reporting of Overdose to the Sponsor, that is not associated with clinical symptoms or abnormal laboratory results.
2. an elevated AST or ALT lab value that is greater than or equal to 3X the upper limit of normal and an elevated total bilirubin lab value that is greater than or equal to 2X the upper limit of normal and, at the same time, an alkaline phosphatase lab value that is less than 2X the upper limit of normal, as determined by way of protocol-specified laboratory testing or unscheduled laboratory testing.*

***Note:** These criteria are based upon available regulatory guidance documents. The purpose of the criteria is to specify a threshold of abnormal hepatic tests that may require an additional evaluation for an underlying etiology. The trial site guidance for assessment and follow up of these criteria can be found in the Investigator Trial File Binder (or equivalent).

3. In the event a subject develops any of the following AEs, a detailed narrative of the event should be reported as an ECI to the Sponsor within 24 hours and to Merck Global Safety within 2 working days of the event:
 - a. Grade ≥ 3 diarrhea
 - b. Grade ≥ 2 colitis
 - c. Grade ≥ 2 pneumonitis
 - d. Grade ≥ 3 hypo- or hyperthyroidism

A separate guidance document has been provided entitled “event of Clinical Interest and Immune-Related Adverse Event Guidance Document.” This document provides guidance regarding identification, evaluation and management of ECIs and irAEs. Additional ECIs are identified in this guidance document and also need to be reported to the Sponsor within 24 hours and to Merck Global Safety within 2 working days of the event.

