Subjects should be assessed for possible ECIs prior to each dose. Lab results should be evaluated and subjects should be asked for signs and symptoms suggestive of an immune-related event. Subjects who develop an ECI thought to be immune-related should have additional testing to rule out other etiologic causes. If lab results or symptoms indicate a possible immune-related ECI, then additional testing should be performed to rule out other etiologic causes. If no other cause is found, then it is assumed to be immune-related.

ECIs that occur in any subject from the date of first dose through 90 days following cessation of treatment, or the initiation of a new anticancer therapy, whichever is earlier, whether or not related to the Merck's product, must be reported within 24 hours to the Sponsor and to Merck Global Safety within 2 working days.

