3.3 Endocrine

The following AE terms, if considered \geq Grade 3 or if \geq Grade 2 and require holding/discontinuation/ modification of pembrolizumab dosing, are considered ECIs and should be reported to the Sponsor within 24 hours of the event:

- Adrenal insufficiency
- Hyperthyroidism
- Hypophysitis
- Hypopituitarism
- Hypothyroidism
- Thyroid disorder
- Thyroiditis

All attempts should be made to rule out other causes such as brain metastases, sepsis and/or infection. However the AE should be reported regardless of etiology.

Hypophysitis or other symptomatic endocrinopathy other than hypo- or hyperthyroidism

Grade 2-4 events:

- Report as ECI if appropriate
- Hold pembrolizumab
- Rule out infection and sepsis with appropriate cultures and imaging.
- Monitor thyroid function or other hormonal level tests and serum chemistries more frequently until returned to baseline values.
- Pituitary gland imaging should be considered (MRIs with gadolinium and selective cuts of the pituitary can show enlargement or heterogeneity and confirm the diagnosis).
- Treat with prednisone 40 mg p.o. or equivalent per day. When symptoms improve to Grade 1 or less, steroid taper should be started and continued over no less than 4 weeks. Replacement of appropriate hormones may be required as the steroid dose is tapered.
- Permanently discontinue for inability to reduce corticosteroid dose to 10 mg or less of prednisone or equivalent per day within 12 weeks.
- Hypophysitis with clinically significant adrenal insufficiency and hypotension, dehydration, and electrolyte abnormalities (such as hyponatremia and hyperkalemia) constitutes adrenal crisis.
- Consultation with an endocrinologist may be considered.

Hyperthyroidism and Hypothyroidism

Thyroid disorders can occur at any time during treatment and within three months of the last dose of pembrolizumab. Monitor patients for changes in thyroid function (at the start of treatment, periodically during treatment, and as indicated based on clinical evaluation) and for clinical signs and symptoms of thyroid disorders.

Grade 2 hyperthyroidism, Grade 2-4 hypothyroidism events:

- Report as ECI if appropriate (see Table 1)
- Monitor thyroid function or other hormonal level tests and serum chemistries more frequently until returned to baseline values.
- Thyroid hormone and/or steroid replacement therapy to manage adrenal insufficiency.

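### Non-serious immune-related events below the ECI thresholds need be recorded only to 30 days after a loosely dated end of treatment, while SAEs and ECIs run to 90 days

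*Combined protocol and SAP*

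**What the plan says.** Safety of the combination, judged by CTCAE adverse events, is one of the primary objectives in 3.1. The recording rules are these.

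- **Ordinary adverse events.** 7.2: "All adverse events will be recorded from the time the consent form is signed through 30 days following cessation of treatment". 5.8 repeats the period after the end of treatment: "each subject will be followed for 30 days for adverse event monitoring". 7.1.5.3.1, on the visit about 30 days after the end-of-treatment visit: "All AEs that occur prior to the Safety Follow-Up Visit should be recorded".
- **Serious events.** 7.2.3.1 runs "through 90 days following cessation of treatment, or the initiation of new anti-cancer therapy, whichever is earlier".
- **ECIs, serious or not.** 7.2.3.2 covers "ECIs that occur in any subject from the date of first dose through 90 days following cessation of treatment", with the same cut at new anti-cancer therapy. 7.2.3.1 has non-serious ECIs handled like SAEs.

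On timing of onset, 5.6.1.1 says: "An irAE can occur shortly after the first dose or several months after the last dose of treatment". The guidance document in 12.6 (its section 3.3) adds: "Thyroid disorders can occur at any time during treatment and within three months of the last dose of pembrolizumab".

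Section 8.2 tabulates safety and adverse events and names no window.

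**The concern.** The protocol describes a period of immune risk that outlasts its ordinary recording window. The longer window is reserved for events that are serious or meet an ECI threshold. A low-grade immune event that starts after day 30 and meets neither condition need not be recorded.

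The date that starts the 30 days is also not fixed. Enzalutamide continues throughout the study and men may spend long periods in monitoring after pembrolizumab. The end of treatment can therefore mean the last pembrolizumab dose or a much later discontinuation. Two staff members could apply different windows to similar patients, and the safety table would then mix follow-up periods without saying so. At stake is whether the reported frequency of low-grade immune events, thyroid events above all, can be read as a rate over a known period.

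**Working it through.** **1. What the 90-day rules leave out.** Under 7.2.3.2 and Table 1 of the 12.6 guidance:

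| Event | ECI threshold | Left to the 30-day rule |
|---|---|---|
| Pneumonitis, colitis, hepatic, ocular, nephritis or renal failure | Grade 2 or higher; for colitis, hepatic and ocular terms also any grade with dose modification or steroids | Most Grade 1 |
| Listed neurologic terms, infusion reactions, severe skin terms, myocarditis, pericarditis, pancreatitis | Any grade | None |
| Thyroid and other listed endocrine terms | Grade 3 or higher, or Grade 2 with dose modification or systemic steroids | Grade 1, and Grade 2 without those triggers |
| Rash, pruritus | Grade 3 or higher, or a rash judged clinically significant | Minor rash, Grade 1-2 pruritus |

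The thyroid row matters most. For Grade 2 hyperthyroidism and Grade 2-4 hypothyroidism the guidance allows pembrolizumab to continue while the thyroid disorder is treated. A Grade 2 event would thus often have neither trigger. 7.1.5.3.1 follows events above Grade 1 to resolution, but that concerns events already recorded, not new ones.

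**2. Which date starts the clock.**

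- 7.2: cessation of treatment, undefined.
- 7.1.5.3.1: the end-of-treatment visit.
- 7.1.1.5.3: the last dose of trial treatment.
- Flow chart (6.1): 30 days after discontinuation.
- 7.1.2.1: recording throughout the study and the follow-up period, with a referral to 7.2 for detail.

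**3. What the choice of date does.** Inputs: four doses every 3 weeks (Table 2), so the last first-course dose is at week 9; 30 days = 30/7 = 4.3 weeks; three months taken as 13 weeks, so the protocol's thyroid window ends at week 9 + 13 = 22.

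| Clock starts at | Recording ends | Uncovered to week 22 |
|---|---|---|
| Last pembrolizumab dose, week 9 | 9 + 4.3 = 13.3 | 22 − 13.3 = 8.7 weeks (8.7/22 = 40%) |
| Discontinuation at week 12 | 12 + 4.3 = 16.3 | 22 − 16.3 = 5.7 weeks (5.7/22 = 26%) |
| Discontinuation at week 18 (progression seen at week 12, confirmed 6 weeks later under 7.1.2.6) | 18 + 4.3 = 22.3 | None |
| Discontinuation later, after monitoring | After week 22 | None |

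**4. Size of any understatement.** The documents give no onset distribution and no late event rate, so this is illustration only. Suppose the clock starts at the last dose and onsets after it are uniform over L days. A 30-day window then sees 30/L of them, and a 90-day window min(90, L)/L:

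- L = 90: 33% against 100%
- L = 120: 25% against 75%
- L = 180: 17% against 50%

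Suppose also that 5% to 20% of the 58 men have a late event below the ECI thresholds: 58 × 0.05 = 2.9 to 58 × 0.20 = 11.6 men. By day 30 about 1.0 to 3.9 of them would be seen if L = 90, and 0.5 to 1.9 if L = 180. With the clock at week 18 or later, no onset in the first 90 days after the last dose would be missed for lack of a window.

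**The case against.** The best defence has four parts.

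- **The 90-day rule covers much of what matters.** A reader might infer that all non-serious events stop being recorded at day 30. They do not: non-serious ECIs run to 90 days and include most organ-specific immune events from Grade 2 and several at any grade. Grade 2 hypophysitis and other symptomatic non-thyroid endocrinopathy are managed with prednisone in the guidance, so they qualify through steroid use. This stands, and it confines the gap to the events listed above.
- **A man in monitoring may not have started the clock.** The flow chart places monitoring and retreatment before discontinuation and puts the safety visit 30 days after it. On that reading his late thyroid event is inside the window. The sentence in 7.2 also continues with recording at each examination, and monitoring visits include one. This is a fair reading, but not the only one: recording at each examination could equally mean within the window, and 7.1.1.5.3 counts from the last dose.
- **Safety is not a listed endpoint.** A reader might infer a biased primary safety outcome. Section 8.1 names only PSA response as the primary endpoint, and 8.2 has no safety test or threshold. Safety is a primary objective, reported descriptively.
- **A tiered 30/90-day scheme is a legitimate choice.** So it is. But the protocol's own account of onset goes beyond 30 days. The flow-chart footnote also lets investigators thin out the marked monitoring tests, thyroid tests among them, only from three months after the last pembrolizumab dose.

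The flow chart's adverse-event review row shows no entry at monitoring visits. Little should rest on this. The table may be broken in extraction, and the row is equally blank for retreatment cycles, where 7.2.3.2 requires ECI assessment before each dose.

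**Conclusion.** The gap is real but narrow. Non-serious immune-related events below the ECI thresholds have a 30-day window, against 90 days for SAEs and ECIs, a difference of 60 days when both clocks start on the same date. The start of that window is not tied to one date. The likely direction is understatement of late low-grade immune events in the 8.2 table, together with uneven recording.

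The size cannot be derived. A reader might take the 40% above as the share of the risk period that is lost. That holds only if cessation of treatment means the last pembrolizumab dose, a reading to which the flow chart and 7.1.5.3.1 give little support. A reader might also want a true rate set against a recorded rate. Any such pair would rest on assumed event rates and onset times.

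The men most clearly affected are those who discontinue soon after the first course and have not yet started new therapy. Table 7 waives confirmation of soft-tissue progression after week 12, so some may stop before week 18. This is a worthwhile, inexpensive improvement and does not touch the PSA analysis.

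**What to change.** - In 7.2, 5.8 and 7.1.5.3.1, record immune-related adverse events, and any event judged related to pembrolizumab, at any grade, through the later of (a) 90 days after the last pembrolizumab dose of any course and (b) 30 days after discontinuation, ending earlier if new anti-cancer therapy starts. The later of the two dates is needed: a bare 90 days from the last dose could shorten recording for men who stay in monitoring.
- Define this clock once, and bring 7.1.1.5.3, 7.1.2.1, 7.1.5.3.1, 7.2, 7.2.3.2 and the flow chart into line with it. Show adverse-event review at the existing monitoring visits.
- For men who have left scheduled visits, collect these events through the contacts already needed for 90-day SAE and ECI reporting. The 12-weekly telephone call in 7.1.5.4.1 now covers survival status only, so an adverse-event question must be added if that call is used.
- State the window, and the date it starts from, in the 8.2 safety table.

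The cost is protocol wording and somewhat more data entry; no new visits or tests are needed. Two limits remain. Asymptomatic laboratory changes after a man leaves scheduled visits will still be missed. Onsets beyond the later date, or after new therapy, stay outside the window.
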